Power Calculation and Data Analysis. We performed a power analysis using serum endotoxin (day 28) as the primary outcome. Mean serum endotoxin of MetS and healthy adults was used to predict a conservative 30% improvement by GTE in MetS persons; this corresponds to a 10 EU/mL decrease in endotoxin in MetS. Simulations were used to estimate power based on 20 healthy and 20 MetS adults randomized to treatment vs control in a 50/50 ratio, respectively. Based on a linear model with treatment and health status, and within-subject measures, we will have >90% power (α =0.05) to detect the primary contrast of interest (GTE vs placebo in MetS adults) and additionally, >85% power (α =0.05) to detect an interaction between treatment and health status. Most data will be analyzed by linear mixed effects models (LMMs) with random effect for subjects (to account for repeated measures) and fixed effects for health status, gender, GTE treatment, time period, and their interactions. Multivariate regression analysis will define correlations between study variables with consideration of potential covariates. Statistical significance for all analyses will be set at P≤0.05.

C. Measurement/Instrumentation

Anthropometric Parameters and Blood Pressure. At screening, participants will rest for 15 minutes prior to determining blood pressure using an automated cuff. BMI will be calculated from height determined from a wall-mounted stadiometer and weight from a calibrated scale. Waist circumference will be assessed at the level of the umbilicus using a nonflexible measuring tape.

Blood Chemistries. At screening, fasting plasma glucose, triglyceride, and HDL-cholesterol will be measured by spectrophotometry utilizing validated clinical assays (Pointe Scientific). At day 0, 14, and 28 of the interventions, collected blood will be sent to The Ohio State University Medical Center for metabolic evaluations by assessing a serum chemistry panel [e.g. [e.g. liver function (aminotransferases), renal function (creatinine, BUN), CBC, glucose, insulin, insulin resistance⁷⁹].

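### Power was stated for a model without gender, but the planned mixed model adds gender and its interactions; if the sexes are uneven, the stated power is not supported under that model.

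*Combined protocol and SAP*

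**What the plan says.** Section III.B, Power Calculation and Data Analysis, takes day-28 serum endotoxin as the primary outcome. The expected effect is a 30% improvement in MetS adults, and "this corresponds to a 10 EU/mL decrease in endotoxin in MetS". The power statement is introduced with "Based on a linear model with treatment and health status, and within-subject measures" and gives two figures. The first is "we will have >90% power (α =0.05) to detect the primary contrast of interest (GTE vs placebo in MetS adults"). The second is ">85% power (α =0.05) to detect an interaction between treatment and health status".

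The next sentence describes the analysis: linear mixed models for most data, with a random subject effect and "fixed effects for health status, gender, GTE treatment, time period, and their interactions". Gender and time period appear only here. The order of the interactions is not limited, and the section does not say how the MetS contrast is formed once gender interacts with treatment.

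Section III.A (Research Design) plans 20 MetS adults and 20 healthy adults matched on age and gender, with block randomization. It states no quota for either sex and no stratification by gender. No SD or within-person correlation for endotoxin is given anywhere.

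**The concern.** The power figures belong to one model and the analysis to another. Once treatment may act differently in men and women, the effect in MetS adults has to be built from a male and a female estimate, and the result depends on the weights. Equal weighting is the usual least-squares-means default. Under it, the smaller sex counts for more than its share and the contrast becomes less precise. Matching carries any imbalance in the MetS group over to the healthy group, so the treatment-by-health-status interaction is affected too.

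The primary question does not need this. Each person receives both treatments and gender is constant within a person, so gender cannot confound the within-person comparison. The open choices of interaction order and weights also leave the analyst discretion over the primary result.

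**Working it through.** **Inputs from the plan (III.A, III.B).** 20 MetS and 20 healthy adults; two-period crossover; effect 10 EU/mL in MetS (10/0.30 implies a MetS mean of about 33 EU/mL); α = 0.05; power above 90% for the MetS contrast and above 85% for the interaction.

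**Assumptions.** Two-sided test, no dropout, day-28 values only, equal variances, zero effect in healthy adults, the same sex split in both groups.

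**Step 1: the plan's own figures.** They cannot be reproduced, because no SD is given. The SD of the within-person GTE-placebo difference (SDd) can be back-solved from the noncentral t with 38 df.

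- MetS contrast: SE = SDd/√20. Power is exactly 90% at SDd = 13.44 (SE 3.01, noncentrality 10/3.01 = 3.33).
- Interaction: SE = SDd·√(1/20 + 1/20). Power is exactly 85% at SDd = 10.28 (SE 3.25, noncentrality 3.08).

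At SDd = 13.44 the interaction has only 63% power. Under these assumptions both stated figures hold together only if SDd is at most about 10.3, where the MetS contrast has 98.9%.

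**Step 2: equal weighting over gender.** With n1 and n2 of each sex among n = 20, SE = SDd·√[(1/n1 + 1/n2)/4]. Relative to the powered model, the variance ratio is n²/(4·n1·n2). At 15:5 this is 400/(4·15·5) = 1.33, an effective sample of 15. The residual df are 36.

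**Step 3: power.**

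| Split | Variance ratio | MetS contrast, SDd 13.44 | MetS contrast, SDd 10.28 | Interaction, SDd 10.28 |
|---|---|---|---|---|
| 10:10 | 1.00 | 89.9% | 98.8% | 84.9% |
| 12:8 | 1.04 | 88.7% | 98.6% | 83.4% |
| 14:6 | 1.19 | 84.3% | 97.2% | 78.3% |
| 15:5 | 1.33 | 80.1% | 95.6% | 73.6% |
| 16:4 | 1.56 | 73.6% | 92.3% | 66.8% |
| 17:3 | 1.96 | 63.8% | 85.6% | 57.0% |

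**Step 4: checks.** With 20,000 simulated trials per scenario, power for the MetS contrast at 15:5 was 79.6% (SDd 13.44) and 95.8% (SDd 10.28). With weights proportional to the sample, power is 89.9% or 98.8% at every split, so only a few degrees of freedom are lost.

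**The case against.** The strongest reply is that the mechanism is not written in the plan. Equal gender weights are a software default, and no software is named for the mixed models. Proportional weights remove the loss. The interaction order is also open: leaving out only the gender-by-treatment-by-health-status term lowers the ratio at 15:5 from 1.33 to about 1.17. The sex split is unknown, nothing in the plan points to a strong imbalance, and 12:8 costs about one point. All of this stands, and it makes the loss conditional. The loss is not bounded from above either: keeping period interactions as well gives 1.38 at 15:5 with sequences split 8/7 and 3/2.

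A second reply is that a reader might infer from the 89/84/80/74% series that the claim of more than 90% fails. The documents do not support that. The series starts from exactly 90%, and the plan's interaction figure implies a smaller SD, at which the MetS contrast stays above 90% through 16:4. An effect in healthy adults, which the Anticipated Results section leaves possible, would shrink the interaction and imply a smaller SD still; unequal group variances could loosen the bound. This reply stands for the MetS contrast, but at that SD the loss moves to the interaction.

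The interaction figure is not shown to fail either, since both figures are stated as lower bounds. If SDd were 8, a 16:4 split would act like an SD of 8·√1.56 = 10.0, where interaction power is about 87%.

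Finally, gender interactions address effect modification, which is a legitimate question. It is a secondary one here.

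**Conclusion.** The point holds in conditional form. The plan states power for one model and analyses with another, and the added gender-by-treatment terms can cost power. The cost is negligible at 10:10 or with proportional weights. With equal weights, the variance of the MetS contrast rises by 4% at 12:8 and by 56% at 16:4. Which stated figure suffers depends on the unreported SD: the MetS contrast if SDd is near 13.4, the interaction if it is near 10.3. The stated power is therefore not supported under the planned model when the sexes are uneven. It would go too far to say that the trial is underpowered for its primary contrast, because the documents give neither the SD nor the sex split needed to show that.

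**What to change.** Specify one primary endotoxin model in section III.B:

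- a random subject effect, with fixed effects for treatment, health status, treatment × health status and phase, and gender as a main effect only;
- either day-28 values only, or all study days with day, treatment × day and treatment × health status × day terms;
- the day-28 GTE-placebo contrast in MetS adults and the day-28 treatment × health status interaction, both taken from that model.

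The day terms are essential if all days are used. Without them the model gives a treatment effect averaged over days 0, 14 and 28: assumed MetS effects of 0, -5 and -10 EU/mL would return (0 - 5 - 10)/3 = -5, not the day-28 value.

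Fit gender-by-treatment interactions in a separate secondary model, with their order and the contrast weights stated. Report the SD and correlation behind the power simulation, and re-run it under the chosen model.

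The cost is plan wording and one repeated simulation; no participants, visits or assays are added. The change should be made before the treatment codes are broken. The downside is that gender-by-treatment results become explicitly secondary.

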In conclusion, evidence shows that 1) limiting gut-derived endotoxin is an antiinflammatory strategy, 2) GTE lowers TLR4/NFκB-dependent inflammation, and 3) GTE improves gut health through improving gut barrier function and alleviating gut dysbiosis. Our team has the expertise and experience to safely perform controlled crossover interventions to assess metabolic parameters, gut barrier

permeability, and gut microbiota composition. Thus, after completing these studies we expect to substantially advance a critically needed strategy to manage disease-promoting, systemic inflammatory responses that are driven by endotoxemia.

Anticipated Results

Preclinical evidence supports the gut-level benefits of catechin-rich GTE to limit metabolic endotoxemia. ^{8,19} We expect these preclinical findings to be translated to similar gut-level improvements in MetS persons utilizing a novel, catechin-rich GTE confection (i.e. snack food). We expect to achieve >95% compliance (based on returned confections and circulating catechins) without any adverse effects or changes in body mass or energy intakes. Based on our mouse studies, ^{8,19} GTE is expected to decrease serum endotoxin in a time-dependent manner, and most substantially among MetS persons due to their endotoxemia. These benefits are expected to occur through an antiinflammatory mechanism that attenuates gut-derived endotoxin translocation. This would be consistent with GTE reducing endotoxin translocation to the portal vein by increasing intestinal expression of TJPs^{8,19} Thus, GTE will decrease small intestinal and colonic permeability, based on decreased urinary excretion of lactulose/mannitol (0-5 h) and sucralose (0-24 h), respectively. ⁴⁶

Similar to our studies, GTE also will alleviate gut dysbiosis that is known to occur in MetS persons (e.g. depleted populations of SCFA-producing bacteria⁴⁷). Selective antimicrobial activities of GTE will decrease LPS-derived Gram-negative bacteria (e.g. *Bacteroides*).^{42,44} GTE will also increase commensal bacteria, including *Clostridia* (Cluster XIV and IV) and other members of the Grampositive Phyla *Firmicutes* that generate SCFAs.^{48,49} This will be corroborated by greater fecal butyrate and other straight chain SCFAs. Thus, these findings would suggest a mechanism, at least in part, that the alleviation of gut dysbiosis restores butyrate generation.

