We will conduct a *randomized double-blind, placebo-controlled crossover trial* in metabolic syndrome (MetS) and healthy individuals. We will enroll adults with (n = 20) and age- and gender-matched healthy (n = 20) men and women (18-65 y). Participants will be block-randomized to receive GTE-rich (1 g GTE) or placebo confections and will be asked to consume the confections daily for 4 wk, while instructed to abstain from all tea varieties and follow a low-polyphenol diet. Blood will be collected at day 0, 14, and 28 for metabolic assessments and safety monitoring by assessing a serum chemistry panel [e.g. liver function (aminotransferases), renal function (creatinine, BUN), CBC, glucose, insulin, insulin resistance 19. At the same time points, blood pressure and anthropometrics will be assessed, and dietary nutrient and flavonoid intakes will be evaluated from 3-d food records using NDSR dietary analysis software and the NCC Flavonoid and Proanthocyanidin database as we described. On day 28, participants will provide a 3-d fecal sample. Following blood collection, they will complete a gut permeability test and collect urine through day 29 (described below). Upon completing these procedures, participants will undergo ~1-mo wash-out before repeating the study identically, but with crossover to the alternate treatment.

GTE-rich Confections. The [name] and [name] labs have previously developed a starch-based GTE-rich confection⁷³ as a successful catechin delivery system. For this application, we will modify this

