Gut Permeability. At wk 4 (d 28), fasted participants will ingest a sugar probe solution [sucrose (40 g), lactulose (5 g), mannitol (1 g), sucralose (1 g), and erythritol (1 g)] as described.⁸⁵ Sucrose-free meals will be provided for 24 h (through d 29). Urinary sugars will be assessed using our established LC-MS method.⁸⁵ Sugar excretion (%), and mannitol-normalized excretion ratios of sugars from 0-5 h and 6-24 h will be calculated to reflect upper and lower GI permeability.⁸⁶⁻⁸⁹ This approach is based on lactulose being absorbed in the small intestine, but not the colon, whereas sucralose is absorbed in the colon; sucrose is used to reflect gastric permeability.⁴⁶ Thus, these studies will define site-specific gut permeability, and benefit of GTE treatment.

Microbiota Composition and Function. Microbiota composition and the predicted functional metagenome will be assessed from fecal samples collected on 3 days at wk 4 (d 25-27), as [name] (co-PD) described. 90-94 Effects of GTE and MetS status on total bacterial abundance will be determined by qPCR. 95 Microbiota will be characterized for diversity and community structure by sequencing 16S rRNA genes using MiSeq. Briefly, one amplicon library (targeting the V3-V4 hypervariable region using bacteria-specific primers) will be prepared by pooling PCR products from three replicate PCR reactions for each sample. Amplicon libraries will be sequenced using the 2x300 pair-ended sequencing reactions. Sequencing reads (≥50,000/sample) will be subjected to quality control to filter out artificial sequences prior to bioinformatics analysis using Qiime. 96 Bacteria will be identified by comparing sequences representing each operation taxonomic unit (OTU) with RDP and Silva databases. ^{97,98} α-Diversity (OTU richness, Shannon-Wiener diversity index, evenness) will be calculated using Oilme. Comparisons of diversity among samples (β-diversity) will be performed using the Bray-Curtis dissimilarity, 99 followed by multivariate analyses (e.g. principle coordinate analysis, permutational multivariate analysis of variance, analysis of similarity, partial least square discriminant analysis). The functional metagenome will be predicted using PICRUSt¹⁰⁰ and PanFP¹⁰¹ based on reference genome databases and the KEGG Orthology classification scheme to obtain a functional gene abundance matrix.

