
In the event that a participant is telephoned and is unavailable, a message will be left requesting a callback at a convenient time or that at a member of the study team will try calling again at a later time. No confidential or sensitive information will be shared with third parties or left on answering machines.

Intervention Timeline. Each participant will complete a 2-phase (GTE vs placebo) randomized, crossover study. Each study intervention will consist of 3 study visits (Day 0, 14, 28) over a 4-wk period. After completing the first intervention, participants will undergo a wash-out period (1 month), and afterwards, begin the alternative intervention.

On Day 0, participants will come to the study center in a fasted state and provide a blood sample (45 mL) to measure endotoxin, TMAO, LBP, sCD14, a panel of clinical chemistries, and catechins. Following the blood collection, participants will be instructed on how to complete a 3-d diet record as well as be informed about maintaining a low-polyphenol diet throughout the duration of the intervention. Participants will then be provided a 2-wk supply of confections, for which they will be instructed to consume 6 confections each day (2 confections/meal; 1 g GTE/d).

On Day 14, participants will return to the study center in the fasted state and return any uneaten confections. Another blood sample (45 mL) will be collected for measurement of biomarkers as described above. Participants will then be asked to complete another 3-d diet record and be reminded to keep maintaining a low-polyphenol diet.

Prior to the final visit on Day 28, participants will collect a stool sample during the preceding 3 days. Participants will collect their stool samples in the comfort of their home and will be asked to return the samples on ice or meet with study personnel to return the samples to the study center within 24 h upon

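### PERMANOVA, ANOSIM and PLS-DA are given no participant-level unit: run sample by sample over both crossover periods, the MetS-versus-healthy test is too liberal and, with one profile per period, the GTE test loses power

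*Combined protocol and SAP*

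**What the plan says.** **Design.** Section III.A has each participant finish one treatment and wash out "before repeating the study identically, but with crossover to the alternate treatment". With 20 MetS and 20 healthy adults, that is 40 people and at least 80 stool profiles.

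**Microbiota analysis.** III.C (Microbiota Composition and Function) frames beta-diversity as a comparison between samples on Bray-Curtis dissimilarity, followed by "multivariate analyses (e.g. principle coordinate analysis, permutational multivariate analysis of variance, analysis of similarity, partial least square discriminant analysis". It states no permutation unit, strata, subject term or cross-validation scheme.

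**Repeated measures.** The only provision is in III.B (Power Calculation and Data Analysis): "Most data will be analyzed by linear mixed effects models (LMMs) with random effect for subjects", with "fixed effects for health status, gender, GTE treatment, time period, and their interactions". Nothing carries that subject effect over to distance-based tests or PLS-DA.

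**Stool days.** III.C says "Microbiota composition and the predicted functional metagenome will be assessed from fecal samples collected on 3 days at wk 4 (d 25-27". III.A says "On day 28, participants will provide a 3-d fecal sample". III.D (Intervention Timeline) says "participants will collect a stool sample during the preceding 3 days". The only pooling described in III.C is of replicate PCR products from one sample, not of days.

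**Use.** II (Anticipated Results) predicts that "GTE also will alleviate gut dysbiosis that is known to occur in MetS persons". Both the GTE contrast and the MetS contrast therefore feed the mechanism claim.

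**The concern.** PERMANOVA and ANOSIM take their reference distribution from shuffling labels. In their ordinary form they shuffle rows, and rows are exchangeable only if independent. Here two rows come from each person.

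- MetS status is constant within a person, so row-wise shuffling counts 40 people as 80.
- Treatment varies within a person, so row-wise shuffling puts between-person variance into the error term and discards the pairing.
- By-sample folds in PLS-DA put one person's profiles in both the training and the test set.

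A community difference between MetS and healthy adults could then be declared where none exists, and a GTE shift visible in the paired data could be missed. Section II criticises an earlier green tea trial because its parallel design limited power; row-wise shuffling would give up that same advantage here.

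**Working it through.** **1. The plan's own figures.** There are none for the microbiota. The stated power (>90% and >85%) is for serum endotoxin and does not bear on this point.

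**2. Direction, one profile per participant-period.** Let ρ be the between-person share of variance (assumed; not in the documents). Relative to what row-wise shuffling assumes, the true variance of a mean contrast on one taxon is

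- MetS versus healthy: 1 + ρ
- GTE versus placebo: 1 − ρ

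For a single normal contrast the actual size is 2[1 − Φ(1.96/√(1 ± ρ))]. At ρ = 0.3, 0.5, 0.7 this gives 8.6, 11.0, 13.3% for MetS and 1.9, 0.6, 0.03% for GTE. Both directions follow from ρ > 0. A statistic summed over many taxa departs further, so the size also depends on the number of taxa.

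**3. Size, by simulation.** 20 + 20 participants, two periods, log-normal taxa with total log-SD 1, relative abundances, Bray-Curtis, 5% level. The 60-taxon runs used 600 null data sets and 299 permutations; the 200-taxon runs used 1000 and 199. All entries are percentages.

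| Between-person share | 0 | 0.3 | 0.5 | 0.7 |
|---|---|---|---|---|
| MetS false positives, free, 60 taxa (PERMANOVA/ANOSIM) | 5/5 | 17/17 | 23/23 | 34/31 |
| Same, 200 taxa | 5/5 | 24/22 | 40/31 | 65/40 |
| GTE false positives, free, 60 taxa (PERMANOVA) | 4 | 0.3 | 0 | 0 |
| Same, 200 taxa | 5 | 0.5 | 0 | 0 |
| GTE power, 0.2 log shift, 60 taxa: free → restricted | – | 17 → 44 | 11 → 51 | 6 → 70 |
| Same, 200 taxa | 67 → 67 | 40 → 87 | 13 → 93 | 3 → 98 |

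The shift is normal across taxa with SD 0.2 in the 60-taxon runs, and ±0.2 with random sign in the 200-taxon runs. Repeat 60-taxon runs spread over about 15-35% for MetS. Permuting whole participants gives 3-6% for MetS. Using the placebo period alone gives 4-6% even with free shuffling. Restricted permutation for GTE gives 4-5%.

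At a 0.3 shift the GTE loss is small with 200 taxa (free 84-98%, restricted 98-100%) but not with 60 (free 71, 66, 44%; restricted 91, 99, 99%).

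**4. GTE-by-status**, 200 taxa, 0.3 shift in MetS only, shares 0.3 / 0.5 / 0.7: free 11 / 1 / 0%; restricted 45 / 68 / 87%.

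**5. PLS-DA with no true difference** (2 components, 10 folds, chance 50%), same shares, 200 taxa. MetS status: 68 / 78 / 88% with by-sample folds, 50-51% with whole-participant folds. Treatment on raw profiles: 33 / 22 / 10% with by-sample folds, which is below chance.

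**6. Three stool days as separate rows.** Let s, p and e be the person, period-within-person and day shares, with s + p + e = 1. The variance ratios become

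- MetS: 6s + 3p + e
- GTE: 3p + e

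The GTE ratio exceeds 1 when 3p + e > s + p + e, that is, when p > s/2. Free shuffling, 60 taxa, 200 data sets, PERMANOVA:

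| s, p, e | MetS ratio | MetS false positives | GTE ratio | GTE false positives |
|---|---|---|---|---|
| 0.6, 0, 0.4 | 4.0 | 96% | 0.4 | 0% |
| 0.5, 0.1, 0.4 | 3.7 | 98% | 0.7 | 0% |
| 0.4, 0.2, 0.4 | 3.4 | 96% | 1.0 | 4.5% |
| 0.3, 0.3, 0.4 | 3.1 | 86% | 1.3 | 17% |
| 0.2, 0.4, 0.4 | 2.8 | 94% | 1.6 | 40% |

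With 200 taxa the GTE rates at person/period shares 0.3/0.3 and 0.2/0.4 were 28% and 56%. Participant-restricted permutation kept the GTE rate at about 3-6.5% with six rows per person.

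**The case against.** The list of methods is introduced as examples in a measurement section. Neither free shuffling nor pooling of periods is written, and a competent analyst may well block by participant or compare MetS with healthy adults in one period. The Anticipated Results are mostly about named taxa and short chain fatty acids, which are scalar and fit the mixed model. The MetS contrast is not randomised, and the protocol treats MetS dysbiosis as already known. The sizes rest on assumed variances and taxon counts.

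All of this stands, and it limits the point to secondary analyses under a stated condition. It does not supply the missing unit: no text requires blocking, and the choice changes the result.

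Three stronger readings are tempting but unsupported:

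- A reader might infer that the plan commits to free shuffling. It leaves the scheme open.
- A reader might infer that false GTE claims will follow. With one profile per period the GTE error rate is below nominal. It rises only if days are separate rows and period variance is more than half the between-person variance.
- A reader might infer that the planned PLS-DA would produce a spurious GTE classifier. On ordinary profiles its by-sample accuracy for treatment falls below chance.

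**Conclusion.** The point holds conditionally. No participant-level unit is written for these methods. In their usual sample-level form on both periods, with one profile per participant-period, the MetS test is anti-conservative, the GTE and GTE-by-status tests lose power, and by-sample PLS-DA accuracy for MetS status is inflated. The directions need only a positive between-person share.

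The sizes are illustrative: MetS false positives of about 15-35% (60 taxa) or 22-65% (200 taxa) at shares of 0.3-0.7. With stool days as separate rows they are about 86-100%. In that case the GTE test can also be too liberal, at about 17-56% where period variance equals or exceeds between-person variance. The documents give no variance, taxon count or microbiota effect with which to narrow these ranges.

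Unaffected are the primary endotoxin outcome, scalar measures in the mixed model, and a MetS comparison within one period using one profile per person. The plan should be changed, but the trial's main conclusion does not depend on it.

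**What to change.** Add to the analysis plan:

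- **Unit.** Form one profile per participant-period from the three stool days, or keep days nested within participant-period in every permutation. Reconcile the three descriptions of the stool sample.
- **GTE.** Permute only within participants, by re-drawing the randomised sequence with the numbers per sequence kept, so that period is respected. With an assumed 0.3 period shift and no GTE effect, independent within-person flips rejected in 1.8-2.5% of data sets, and re-drawn sequences in 4.5-6.5%.
- **MetS status.** Permute whole participants, or test participant means or a single period.
- **GTE-by-status.** Test within-person differences, permuting status across participants within sequence (false positives 2.5-5.7% in simulation).
- **ANOSIM.** Apply the same restrictions.
- **PLS-DA.** Use the multilevel form (profiles centred within person) for treatment, and leave out whole participants in every cross-validation. The fold rule must come with the centring: on centred null data, by-sample folds gave 95% accuracy and whole-participant folds 49-51%.

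The cost is a few sentences and a permutation-blocking option, with no new data. Combining the days gives up day-to-day detail; nesting them does not.
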